## **Abstract**

**Background:** Scoliosis is the most common orthopedic comorbidity in Rett syndrome (RTT), with a prevalence of 94% and a mean curve progression of 14-21° Cobb annually. A scoliosis prevention intervention based on daily activity programs was proposed for people with RTT within uncontrolled study designs.

**Aim:** The current study aims to evaluate the effectiveness of a home-based activity program carried out during daily life to slow the progression of scoliosis in girls with RTT.

**Ethics:** The proposal was approved by Ariel university IRB. All participants' parents will sign informed consent forms.

**Participants:** Twenty Italian girls aged between six and 16 years with a genetically confirmed classic RTT and scoliosis at a severity level between 10° and 40° Cobb will be recruited and randomly divided into two groups (immediate intervention – Group 1; wait-list-intervention – Group 2). Both groups will follow the same 10-month intervention program, 10 months apart.

**Outcome measures:** Participants' scoliosis Cobb's angle, motor functioning, and behavioral characteristics will be assessed three times.

**Procedure:** The interventions will comprise daily home-based activity programs carried out by participants' caregivers within everyday living environments. An expert therapist will remotely supervise each program through an ad hoc developed smartphone application.

Appendix 7 - Rett Syndrome Behavior Questionnaire (RSBQ)	

## Introduction

Rett syndrome (RTT) is a severe neurodevelopmental disease caused by a mutation in the MECP2 gene located on the X chromosome,[1] affecting about 1/10,000 females worldwide.[2–4] Scoliosis is the most common orthopedic comorbidity in RTT,[5–7] showing a prevalence of up to 94%.[7–11] Reported median age of scoliosis onset in RTT is at 9.8 years, with 25% of subjects affected by the age of 6 years, about 79% by the age of 13 years, and 85% by the age of 16 years or older.[7,9,12,13] Scoliosis in RTT is neurogenic in origin and can result in pain, loss of sitting balance, deterioration of motor skills, and progressive restrictive lung disease development.[14] Diminished early development, inability to sit and walk without support, the onset of puberty, and enhanced clinical severity are also associated with developing scoliosis at an early age.[11,13,15]

The case literature suggests a fast mean curve progression in this population ranging from 14° to 21° Cobb per year, accompanied by an acceleration in the progression at puberty with an average age of 13 years.[11,14,16] Moreover, in a large cohort study analyzing radiographs of 128 girls and women with RTT followed for two years (three radiographs for each subject), the magnitude of scoliosis was found to generally increase with age with a yearly 0.438-unit increase in the square root of the baseline Cobb's angle (95% Confidence Interval 0.374 – 0.503).[17]

A corset is usually suggested for individuals with RTT with Cobb's angle greater than 20-25°, and spinal fusion is considered if Cobb's angle progresses over 40-50°.[12,15,18]

Spinal surgery is considered the definitive management of neuromuscular scoliosis.[19] In most cases, posterior-only spinal fusion is performed.[20] However, if an anteroposterior surgery is required, a single-stage approach is preferable to reduce anesthetic and surgical complications.[12] Fixation to the pelvis is indicated in non-ambulant children with pelvic obliquity[12] and in the presence of a preceding rapid decline in neurological function with a lethargic presentation and uncontrolled, treatment-resistant daily seizures.[21] Surgery should not be delayed until skeletal maturity has been achieved. Barney and colleagues suggested the need for RTT-specific postoperative pain management.[22] The authors reported that, after spinal fusion, patients with RTT received fewer total doses of opioids compared to girls with cerebral palsy and idiopathic scoliosis. With modern technology, severe curves can be safely treated,[21] and positive outcomes following spinal surgery were reported.[23–26] Even so, the decision to perform the operation is challenging for the family due to anxiety about their daughter undergoing such a complex medical procedure.[8,24] Moreover, a large cohort study reported that 18.5% of subjects with RTT

and scoliosis had spinal instrumentation,[15] showing that the vast majority of this group of clients will not undergo surgery and therefore will rely on non-surgical, conservative treatment. Thus, the development and evaluation of such programs are critical for individuals with RTT.

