## **Sample Size and Power Calculation**

The information available in the literature suggests that the Cobb angle in RTT typically increases by approximately  $14 \pm 8^\circ$  Cobb per year. Based on these data, an alpha of 0.05 and a beta of 0.8, we estimate that for this study, the researchers will need a sample size including two groups of 10 subjects and that statistical significance will be achieved if both groups of participants will show an average increase in the scoliotic curve of less than  $12^\circ$  Cobb after the implementation of the proposed program.

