## **Inclusion Criteria**

- Diagnosis of RTT with confirmed MECP2 gene mutation;[40]
- Diagnosis of unstructured flexible scoliosis (Cobb angle between  $10^\circ$  and  $40^\circ$ ) measured radiologically with an x-ray performed no more than six months before the recruitment;
- Age between 6 and 16 years.

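### The 14° per year planning rate is not reconciled with the protocol's own cohort (about 3.0–5.7° per year for 10–40° curves), and a mean rise below 12° shows no programme effect at either rate

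*Combined protocol and SAP*

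**What the plan says.** The Introduction gives two natural-history figures. The first is "The case literature suggests a fast mean curve progression in this population ranging from 14° to 21° Cobb per year". The second comes from radiographs of 128 girls and women followed for two years with three films each, and is a "yearly 0.438-unit increase in the square root of the baseline Cobb's angle (95% Confidence Interval 0.374 – 0.503".

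Sample Size and Power Calculation uses only the low end of the first. It states that the angle "typically increases by approximately $14 \pm 8^\circ$ Cobb per year", takes "an alpha of 0.05 and a beta of 0.8", and arrives at "two groups of 10 subjects". It adds that statistical significance will be achieved if both groups show an "average increase in the scoliotic curve of less than $12^\circ$ Cobb" after the programme. The cohort is not mentioned there.

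The Inclusion Criteria admit curves of 10° to 40° and ages 6 to 16. Study Protocol sets each intervention phase at 10 months. The Statistical analysis section compares the groups on their T1–T2 and T2–T3 changes and contains no test against 12°.

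**The concern.** The planning rate describes Rett syndrome in general, whereas the trial enrols mild to moderate curves. The cohort rate is on the square-root scale, so it can be applied to the eligible range, and there it gives a much slower mean progression than 14° per year. The plan offers no reason for preferring one figure to the other.

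Two things follow. If girls without the programme would on average stay under 12° over the phase, then both groups staying under 12° says nothing about the programme, yet the section presents it as the condition for significance. And if expected progression is only a few degrees, 10 per group may be far too few to detect even a full halt, while the section leaves the reader with a claim of 0.8 power.

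**Working it through.** **Inputs.** Planning rate 14° per year, SD 8°, alpha 0.05, 10 per group, benchmark 12° (Sample Size and Power Calculation). Cohort rate k = 0.438 per year, 95% CI 0.374 to 0.503 (Introduction). Baseline b = 10° to 40° (Inclusion Criteria). Phase length 10 months (Study Protocol). The stated beta of 0.8 is read as power 0.8. The SD is given beside a yearly rate, and using it for a 10-month change is an assumption.

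**1. The plan's own sample size.** Taking the difference as 14 − 12 = 2° and SD 8°, two-sided:

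n per group = 2 × (1.960 + 0.842)² × (8/2)² ≈ 252 (198 one-sided).

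Ten per group gives power of about 0.08 (0.14 one-sided). Taking beta 0.8 literally, as power 0.2, still needs 41 per group. The stated 10 per group is therefore not reproduced. The difference it can detect with 80% power is

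8 × √(2/10) × (1.960 + 0.842) = 10.0° (10.6° by the t-test),

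and the section does not state such a difference.

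**2. Cohort rate applied to eligible curves.** Rise over t years = (√b + k·t)² − b. For example, at 40° over one year: (6.325 + 0.438)² − 40 = 5.73°.

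| Baseline | One year (CI limits) | 10 months (CI limits) |
|---|---|---|
| 10° | 2.96° (2.51–3.43) | 2.44° (2.07–2.83) |
| 25° | 4.57° (3.88–5.28) | 3.78° (3.21–4.37) |
| 40° | 5.73° (4.87–6.62) | 4.75° (4.04–5.48) |

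The planning rate is 14/5.73 = 2.4 to 14/2.96 = 4.7 times the cohort mean. A mean rise of 14° in a year from 40° needs √54 − √40 = 1.02 units, about twice the upper confidence limit. Reading the cohort figure instead as 0.438 × √b gives less still: 1.4° to 2.8° per year.

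**3. The 12° benchmark.** At the plan's own rate, 14 × 10/12 = 11.7°, already below 12°. With SD 8° the standard error of a 10-girl mean is 8/√10 = 2.53°. The chance that a group without any programme effect averages under 12° is then:
- expected mean 11.7°: 0.55;
- expected mean 4.75°: 0.998;
- expected mean 2.44°: above 0.999.

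**4. What complete arrest would show at the cohort rate.** For differences of 2.4° to 4.75° with SD 8° and 10 per group, two-sided power is 0.10 to 0.26 (0.10 to 0.24 by the t-test). The SD may be smaller if progression is slower. For 80% power the SD would have to be δ/(√0.2 × 2.80), that is 2.44/1.25 ≈ 1.9° to 4.75/1.25 ≈ 3.8°.

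**The case against.** The strongest reply is that the cohort may not represent these girls. It includes women, the protocol gives neither its ages, baseline angles nor treatment, and the Introduction reports acceleration at puberty, around 13, inside the 6–16 window. This stands. A reader might infer that 14° per year is wrong for the eligible population. The documents show only an unreconciled conflict, and the cohort cannot be called untreated.

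A reader might also infer that no eligible girl could progress by 14° in a year. That confuses a mean slope with a limit on individuals. With SD 8° around annual means of 2.96° to 5.73°, about 8% to 15% of girls would exceed 14°.

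Nor is arrest a ceiling on benefit. The Background describes one child whose curve fell from 30° to 20° over 18 months, and Importance of the Research contemplates reduction in some cases. The evidence is thin, but 2.4–4.8° should not be presented as the largest possible difference.

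Finally, the randomised comparison does not depend on 14° or 12°: the wait-list group estimates progression directly. That is correct and confines the problem to the sample-size section and to any reading of results against 12°.

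Two limits apply to the 11.7° figure. It assumes 10 months between films, but Scoliosis Progression accepts a baseline film up to six months before the intervention starts. At 16 months the planning rate gives 14 × 16/12 = 18.7°. The cohort rate gives 4.0° at 10° and 7.7° at 40° (k·t = 0.584), still under 12°. And if 12° was meant as a yearly figure, 14° lies above it, although a group mean under 12° would still occur by chance with probability 0.21.

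**Conclusion.** The point holds as an unreconciled planning assumption and an unsound benchmark. For 10–40° curves the cohort implies a mean of about 3.0–5.7° per year, or 2.4–4.8° over 10 months (2.1–5.5° across its confidence limits), against 11.7° from the planning rate. Both lie under 12° over a 10-month interval, so the stated condition for significance can be met with no programme effect, and it matches no test in the Statistical analysis section.

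This assumes that the square root of the angle rises linearly by 0.438 per year, that the cohort mean carries over to ages 6–16, and, for the power figures, that SD 8° applies to 10-month change. It does not establish that 14° is wrong or that the randomised contrast is invalid.

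**What to change.** In Sample Size and Power Calculation:

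1. Delete the statement that significance will be achieved if both groups increase by less than 12°.
2. Give expected 10-month progression without the programme as a range, from about 2.4–4.8° (cohort) to 11.7° (14° per year). State the cohort's limits: women included, age and treatment unstated, acceleration at puberty. Note that an older baseline film lengthens the interval.
3. Replace the 0.8 power claim with what 10 per group delivers at SD 8° and two-sided alpha 0.05: 80% power only for a between-group T1–T2 difference of about 10–10.6°; about 8% for 2° (14 versus 12); and about 10–26% for complete arrest at the cohort rate. Add that arrest is not necessarily the largest possible effect. Changing the rate while keeping the power claim would create a new contradiction.
4. State that the conclusion rests on the randomised between-group comparison of T1–T2 change.

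This is rewording only, with no change to enrolment or procedures. The cost is that the stated power becomes less favourable.

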### **Background**

Available conservative interventions for scoliosis include observation and monitoring, bracing, orthotics, and physical therapy.[27–29] As specific guidelines for the management of scoliosis for people with RTT were published,[12] the available treatments for scoliosis were here described in the light of such guidelines. The scoliosis monitoring for these patients should start before the diagnosis of scoliosis. Before-diagnosis monitoring strategies for people with RTT include genetic testing, parental teaching on the characteristic aspects of scoliosis, and physical assessment upon the diagnosis of RTT and at least every six months thereafter.[12] After diagnosing scoliosis, yearly spine radiographs are suggested to monitor the curve progression. The collection of radiographs every six months is recommended if Cobb’s angle progresses over 25° before the skeletal maturity. The maintenance of physical examinations every six months is advised after the scoliosis diagnosis.[12] Bracing strategies were suggested in the literature for neuromuscular scoliosis management among its conservative treatments. A recent literature review identified 23 typologies of braces proposed to care for scoliosis curves of different types (“C” or “S” shaped), levels (thoracic, lumbar, and thoracolumbar), and entities, using different approaches (passive and active correction).[30] Indications for bracing are stronger in younger children and more controversial in adolescents. Bracing aims to contain the curve until skeletal maturity[31] and regain the sitting position.[32] However, the role of bracing in patients with neuromuscular scoliosis is contentious, and there is no compelling evidence supporting the use and success of braces in preventing the deformity progression in neuromuscular scoliosis.[19,32] There is no consensus among experts on RTT that bracing is beneficial in reducing the scoliosis progression in this population.[12] Nevertheless, bracing may be valuable if support is needed in a sitting position (usually for extremely hypotonic children who find it difficult to maintain an erect posture for long periods) or delay the necessity of surgery.[12,33,34]

When considering conventional interventions regarding scoliosis, there is a consensus among experts that efforts should be made to maintain the ability to walk and increase the duration and distance walked to counteract the curve progression.[19,27,35] However, the capacity of physical therapy treatments to reduce scoliosis or prevent mild scoliosis from

rapidly progressing has received scarce consideration in the literature.[35] Although so far, physical therapy interventions have not been found to improve etiological factors for neuromuscular scoliosis or prevent progression of established scoliosis, they were reported as helpful in avoiding any adverse effects, such as: prolonged brace use, prevention or prolonging onset of joint contractures, and maintenance of both chest mobility and respiratory excursion.[27,32] The implementation of physical therapy for scoliosis must be based on the particular spinal deformity characteristics and requires specifically trained therapists and clinicians.[28]

To our knowledge, only one anti-scoliotic physical therapy intervention explicitly directed to patients with RTT was proposed in the literature.[35] This is a specific physical therapy regimen comprised of an intensive program of postural positioning and enhanced activity level carried out in cooperation with the participant's family members and caregivers (within the educational facility). The intervention was conducted with a 5-year-old girl with RTT whose Cobb's angle reduced from 30° to 20° over an 18-month treatment period through the use of positioning equipment, postural strategies (activating automatic equilibrium reactions, which oppose the natural scoliotic curve), and a motor activity program (walking or standing) during waking hours. This result was maintained for three years until the routine mentioned above ceased, when the child's scoliosis rapidly regressed. A recently published article from Romano et al. [36] replicated this intervention method with 20 participants with RTT in Italy and reported no change in scoliosis severity for this group of clients during a one-year follow-up. Thereby strengthening the validity of the approach proposed by Lotan, Merrick, and Carmeli.[35] Moreover, previous programs were found helpful in increasing the motor function of five girls with RTT in Ireland,[37] 17 girls and women with RTT in Italy,[38] and 40 individuals with RTT in northern Italy.[39] This accumulation of evidence provides initial evidence of the feasibility and acceptability of this type of treatment in a broad age range and a wide functional range of participants.

The intervention proposed in the current protocol is ecological and intensive in nature, will be carried out by primary caregivers within the participants' daily living environment (home and educational facility), and will be planned and supervised by therapists experienced in treating individuals with RTT. Moreover, the authors will remotely supervise the intervention by using an ad hoc developed smartphone application.

## **Study Aim**

The current study aims to evaluate the effectiveness of an anti-scoliotic physiotherapy program carried out during daily life and focuses on hypercorrective postures and on increasing the level of activity to assess whether or not it is possible to slow the progression of scoliosis in girls with Rett syndrome (RTT).

The current research project has the following research objectives:

- Primary objectives:
  1. Build, implement and evaluate a physiotherapy program for contrasting scoliosis trajectory adapted to individuals with RTT;
  2. Develop a secondary deformity prevention program through early intervention for people with RTT.
- Secondary objectives:
  1. Build and evaluate the efficiency of a support application for carrying out rehabilitation exercises;
  2. Explore the factors influencing adherence and implementation of intervention from the perspective of both families and therapists in light of the above-mentioned application.

## **Research Questions**

- Can an individualized, remotely supervised physiotherapy program contrast the scoliosis progression of girls with RTT?
- Can a smartphone application support the adherence and the implementation of an individualized activity program carried out at home by caregivers of girls with RTT?
- Can the use of the application reduce the costs of remote supervision?
- Which factors influence the adherence and implementation of the intervention from the perspective of both families and therapists?

## **Materials and Methods**

### **Study Design**

A randomized controlled study with a waiting list design will be applied.

## **Study Population**

For this study, 20 girls aged between six and 16 years with genetically confirmed classic RTT and scoliosis will be recruited from the San Paolo Hospital (Milan, Italy) or the Italian Rett Association (AIRett – Verona, Italy).

## **Sample Size and Power Calculation**

The information available in the literature suggests that the Cobb angle in RTT typically increases by approximately  $14 \pm 8^\circ$  Cobb per year. Based on these data, an alpha of 0.05 and a beta of 0.8, we estimate that for this study, the researchers will need a sample size including two groups of 10 subjects and that statistical significance will be achieved if both groups of participants will show an average increase in the scoliotic curve of less than  $12^\circ$  Cobb after the implementation of the proposed program.

## **Inclusion Criteria**

- Diagnosis of RTT with confirmed MECP2 gene mutation;[40]
- Diagnosis of unstructured flexible scoliosis (Cobb angle between  $10^\circ$  and  $40^\circ$ ) measured radiologically with an x-ray performed no more than six months before the recruitment;
- Age between 6 and 16 years.

## **Exclusion Criteria**

- Presence of psychomotor developmental deficit evidenced in the first six months of life or diseases of neurometabolic, infectious, or secondary brain damage trauma origin;
- Previous surgical intervention to the spine or its planning within the study period;
- Use of a corset during most waking hours;
- Clinical judgment of the evaluating specialist doctor who certifies unstable health conditions that are not compatible with the performance of the rehabilitation program (e.g., ongoing or recurrent infections, severe gastrointestinal disorders, drug-resistant epilepsy with multi-day seizures).
- Clinical judgment of the research team suggesting an inability of the home environment to perform the intervention program (change in residence, a planned pregnancy, a pre-planned complex surgical/medical procedure within the period of the planned intervention program for the child of family member) within the intervention period.

## **Ethical Issues**

The Ariel University Institutional Review Board (IRB) approved the study (no. AU-HEA-ML-20201019 – See IRB approval in Appendix 1) that will be conducted according to the ethical principles of the Helsinki Declaration and local regulations. All details relating to the study procedure will be discussed with participants' parents or legal representatives, and an informed consent form (See Appendix 2) will be signed for all. Enrolment will be voluntary, with participants not receiving any incentives, financial or otherwise, for participation.

## **Study Protocol**

The participants' parents will receive an information sheet regarding the study and informed consent for participation and collection of video materials at the recruitment. A reference telephone number and an e-mail address will be provided to be contacted in case they would like further information or would like to communicate the exit from the study. The eligibility of the candidates will be assessed at the time of recruitment (T1) through an initial neurological or physiatrist evaluation. At the same time, each participant will undergo a rehabilitation evaluation to collect the outcome measures (see section "Data collection") and create an individualized intervention plan specific to the participant's scoliosis, functional abilities, and parental/educational setting's availability. During the evaluation, the postural needs of the participants will also be identified, and a qualified technician will build or adjust the positioning devices, making them suitable for each intervention plan. Using block randomization, participating girls will be randomly divided into treatment (Group 1) or delayed treatment (Group 2) groups. Participants in Group 1 will begin carrying out the rehabilitation program immediately after the first assessment session (T1). Each program will require the daily performance of different postures and therapeutic activities at the girls' educational facilities and homes, based on the availability of families, for a duration of 10 months. Specific strategies that will be implemented will include maintaining asymmetrical postures that oppose the scoliosis curve during activities and exercises in sitting, standing, and walking positions (according to each participant's functional abilities). These strategies refer to a hypercorrective postural positioning of scoliosis. In addition, activities involving weight bearing on the lower limbs, such as walking and standing for at least two hours a day, will be encouraged, and passive stretching and spinal mobilization exercises will be conducted.

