### **Statistical analysis**

The normality of each variable's distribution will be assessed using the Shapiro-Wilk normality test. The ages, amount of received physical rehabilitation interventions, scoliotic curve degrees, behavioral characteristics, and activity and gross motor functional levels obtained at T1 will be compared between the two groups to assess their comparability through Wilcoxon's signed-rank test or Student's T-test (dependent of the variable distribution characteristics). Changes that occurred in the variables of each group at T1, T2, and T3 will be evaluated with Friedman's test or with the repeated measure ANOVA (dependent on the variable distribution characteristics). Between groups comparison for each variable collected at T1, T2, and T3 and for their variations that occurred between T1 and T2 and between T2 and T3 will be conducted using the Wilcoxon's signed-rank test or Student's T-test (dependent of the variable distribution characteristics), applying an appropriate adjustment for the age and gross motor skills of the participants. Relations will be searched between variables collected at T1 and the changes in the scoliosis curve degree and motor functioning after the treatment using Spearman's rank correlation coefficient or Pearson's correlation coefficient (dependent on the variable distribution characteristics). Moreover, a relation between the compliance with the proposed program and the changes in the scoliosis curve degree and motor functioning after the treatment will be searched using the Spearman's rank correlation coefficient or Pearson's correlation coefficient (dependent on the variable distribution characteristics). The threshold for significance of the above-described analyses will be set at  $\alpha = 0.05$ . No correction for multiple comparisons will be applied.[48]

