### Appendix 3 – Research timetable

- A. Organize the research: gather the participants, obtain the IRB approval in Italy, and prepare the forms.
- B. Evaluation of each participant. Construction of the individualized equipment for postural alignment and a workshop for parents / caregivers / therapists from Group 1 (one week).
- C. Start of the intervention for Group 1.
- D. Intervention in progress for Group 1 with supervision via Skype calls and Group 2 waiting-list phase.
- E. Evaluation of each participant.
- F. Construction of the individualized equipment for postural alignment and a workshop for parents / caregivers / therapists from Group 2 (one week).
- G. Start of the intervention for Group 2.
- H. Intervention in progress for Group 2 with supervision via Skype calls and Group 1 follow-up.
- I. Evaluation of each participant.
- J. Summary of results.

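### With 10 girls per group, allocation is not balanced on prognostic factors, T1 Cobb is left out of the adjustment, and the listed tests cannot carry covariates

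*Combined protocol and SAP*

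**What the plan says.** - **Allocation (Study Protocol).** "Using block randomization, participating girls will be randomly divided into treatment (Group 1) or delayed treatment (Group 2) groups". Block size, stratification factors, minimisation and concealment are not described.
- **Size (Sample Size and Power Calculation).** "the researchers will need a sample size including two groups of 10 subjects".
- **Entry range (Inclusion Criteria).** Ages 6 to 16 years and curves of 10° to 40°.
- **Baseline check (Statistical analysis).** Age, therapy received, curve size, behaviour and motor level at T1 "will be compared between the two groups to assess their comparability", by Student's t or Wilcoxon signed-rank test.
- **Adjustment (Statistical analysis).** The between-group comparisons at T1, T2 and T3, and of the changes between visits, are to be adjusted for age and gross motor skills. T1 Cobb is not named, and the tests are the same two.
- **Order of events.** The Study Protocol section describes the T1 evaluation before it describes randomisation. Appendix 3 lists gathering the participants, then "Evaluation of each participant. Construction of the individualized equipment for postural alignment" together with a Group 1 workshop, then the Group 1 start. No sentence says that allocation waits for all T1 evaluations.

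**The concern.** Blocks equalise numbers, not prognosis. In 20 girls spread over a wide range of age and curve size, the groups can easily differ at the start. Two safeguards are offered, and both are weak.

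A T1 significance test in 10 against 10 misses most imbalances of moderate size, so a non-significant result would be read as comparability when it shows little. The covariate adjustment omits the outcome's own baseline and has no model that could hold it. A starting difference in curve size would therefore pass straight into the raw T2 and T3 Cobb comparisons. The comparison of T1–T2 changes could then give a different answer, and no rule says which one counts.

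**Working it through.** **1. The plan's own figure.** The sample-size section gives "an alpha of 0.05 and a beta of 0.8" (read here as 80% power), natural progression of 14 ± 8° per year (8 taken as the SD) and an average increase below 12°. The implied difference is 2°. For two independent means, n per group = 2 × 8² × (1.960 + 0.842)² / 2² ≈ 252 (two-sided). With 10 per group, power for 2° is about 8%. The stated 10 per group is not reproduced. I use 2° below only as a yardstick.

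**2. Imbalance in a baseline variable.** The SE of a standardised difference is √(2/10) = 0.447.
- One variable: P(|d| > 0.5) = 2 × [1 − Φ(0.5/0.447)] = 0.264.
- At least one of three independent variables (T1 Cobb, age, RESMES): 1 − 0.736³ = 0.60. With mutual correlation 0.5 (assumed) it is 0.54.

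**3. Imbalance in raw T1 Cobb.** The baseline SD is not given. I assume 5° to 8.66°, the upper value being a uniform spread over 10° to 40°. SE = SD × 0.447.

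| SD | SE | P(difference of 2° or more) |
|---|---|---|
| 5° | 2.24° | 37% |
| 7° | 3.13° | 52% |
| 8.66° | 3.87° | 61% |

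**4. What the T1 tests can see.** With 18 df the critical t is 2.101, so only an observed difference above 2.101 × 0.447 = 0.94 SD reaches p < 0.05. Power against a true difference of 0.5 SD is 18.5%.

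**5. Effect on Cobb change.** If baseline factors together explain a share R² of the variance of change (SD 8°), the SE of the imbalance in predicted change is 8 × √R² × 0.447.

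| R² (assumed) | SE | P(2° or more) |
|---|---|---|
| 0.09 | 1.07° | 6% |
| 0.25 | 1.79° | 26% |
| 0.50 | 2.53° | 43% |
| 0.69 | 2.97° | 50% |

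For curve size alone, the Introduction gives a yearly rise of 0.438 in the square root of the angle, or 0.438 × 10/12 = 0.365 over 10 months. A 10° curve then gains (√10 + 0.365)² − 10 = 2.4°, and a 40° curve gains 4.8°. With curves uniform over the entry range, the SD of the between-group imbalance in this expected gain is 0.29°, and P(2° or more) is about 0.

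**6. What balancing would do.** Simulation with three independent, equally weighted covariates; P(at least one differs by more than 0.5 SD):
- blocks of 4: 60%
- minimisation on median splits, with probability 0.8 of the balancing choice: 37%
- constrained randomisation within the best-balanced 10% of allocations: 0%

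P(raw T1 Cobb differs by 2° or more), at SD 8.66°, is 61%, 49% and 13% respectively.

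**7. Price of covariates.** With q normally distributed covariates and N = 20, chance imbalance multiplies the variance of the adjusted difference by 1 + q/(N − q − 3) on average. This is 1 + 2/15 = 1.133 for the two covariates already planned and 1 + 3/14 = 1.214 for three. Residual df fall from 18 to 15. Ignoring the small change in critical t, three covariates repay their cost when together they explain more than 1 − 1/1.214 ≈ 18% of the outcome variance.

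**The case against.** Block randomisation is a valid method. Chance imbalance is already allowed for in the standard error and does not raise the type I error rate. The plan also adjusts for two of the three obvious factors, and comparing changes subtracts the starting curve. All of this stands. It limits the point to precision and to the missing baseline covariate and model.

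A reader might infer that an imbalance as large as the planned effect is likely. The documents do not support that for Cobb change. The 60% is the chance that some baseline factor differs by 0.5 SD, not the chance of a 2° shift in outcome. That shift passes 50% only when R² is near 0.69, and the square-root model puts it near zero for curve size alone. The Introduction links poor sitting and walking and greater severity to early onset of scoliosis; only puberty is tied to faster progression. The 2° yardstick is itself loose, because the 12° is a threshold for "both groups of participants will show an average increase in the scoliotic curve of less than" that value, not a stated between-group difference.

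A reader might also infer that all T1 data are in hand before allocation and that balancing is free. The order of the text suggests the first but does not state it. The Study Protocol has Group 1 begin directly after T1, which can be read girl by girl, and the time of the three blinded Cobb readings is not given. On the second, waiting for the last evaluation has a cost.

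**Conclusion.** The point holds as a matter of precision and of an incomplete analysis model. Nothing but group size is balanced. A difference above 0.5 SD in at least one of three main baseline variables is more likely than not (60% if independent, 54% at correlation 0.5), and a difference of 2° or more in mean T1 Cobb has probability 37% to 61% over the assumed SDs. To the extent that curve size persists, this enters the raw T2 and T3 comparisons uncorrected. The T1 tests cannot rule it out.

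How far it moves the comparison of changes depends on how prognostic the factors are. The documents quantify this only for curve size, where the implied effect is small. Balancing would not repair the mismatch between 20 girls and a 2° difference.

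**What to change.** 1. **Analysis.** Compare T1–T2 Cobb in one linear model (ANCOVA) with group, T1 Cobb, age and RESMES. Once T1 Cobb is in the model, analysing the T2 value or the change gives the same group effect, so the two cannot disagree. All the data are already collected. The cost is one covariate beyond the two planned: average variance factor 1.214 instead of 1.133, before any gain from what T1 Cobb explains.
2. **Baseline table.** Replace the T1 significance tests by a descriptive table with standardised differences. No cost.
3. **Allocation, a cheap addition.** State that allocation follows completion of the T1 evaluations, as the order in Appendix 3 suggests, and reconcile this with the Study Protocol sentence on when Group 1 begins. Then make one concealed draw by constrained randomisation on eligibility or T1 Cobb, age and RESMES. Using the eligibility Cobb avoids waiting for the three-reader mean. Minimisation is possible but balances less well here (37% against 0% in step 6).

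Item 3 needs a short script and a few protocol sentences. Its downside is that Group 1 waits for the last T1 evaluation, so the six-month X-ray window in the Scoliosis Progression section must still be met. The balancing variables must also stay in the analysis. If item 3 is declined, items 1 and 2 are the minimum.
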